### **3.3.5.5 Gastrointestinal adverse effects**

In studies, minor symptoms of the gastrointestinal tract, such as abdominal cramps, nausea, soft stools, flatulence and distortion of taste sensations, were recorded against the background of probiotic therapy. Nevertheless, according to a meta-analysis and a systematic review of the use of probiotics aimed at prevention of diarrhea caused by *Clostridium difficile*, the probability of developing these adverse effects is 18–20% lower in patients receiving probiotics than in control individuals (Johnston et al. 2012; Goldenberg et al. 2013)

## **3.4 A brief description of the known and potential risks and benefits to research subjects, if there are any**

Preclinical and clinical studies of the components of the products planned for use in this study indicate a good safety profile and good tolerability of LRG-002, capsules. A list of known adverse effects of these products is presented in section 3.2.

During the study, venous blood is supposed to be taken for analysis - about 12 ml (about 1 tablespoon) on day 1, day  $7 \pm 2$  and day  $15 \pm 2$ , i.e. the total volume of blood that will be taken for the study shall not exceed 36 ml for the entire period of the study. This is a clinically insignificant amount and rate of blood loss for an adult without severe concomitant diseases. Potentially, a bruise or hematoma is possible due to venipuncture, as well as the development of phlebitis or thrombophlebitis at the injection site.

The research center staff will make every possible effort to minimize the risks for patients associated with the research procedures and treatment within the study. In the case of adverse events or other health problems, the patient will be provided with the necessary medical care.

The benefits of participating in the study are related to the possibility of conducting a series of laboratory and instrumental examinations, treatment under the supervision of highly qualified doctors, and treatment with the investigational drugs free of charge for the study participant.

### **3.5 Description and justification of the method of administration, dosage, dosing regimen and course of treatment**

#### **3.5.1 Description and justification of the method of administration, dosage, dosage regimen and course of treatment with the investigational drug**

To achieve a positive effect, probiotics should be taken in sufficiently high doses. The proposed dose of *Lactobacillus rhamnosus* GG is within the range of doses that have proven effective in well-planned and conducted randomized controlled trials described in the metanalysis Szajewska, 2015, Hempel, 2012, McFarland, 2006, as well as in the studies, carried out by Vanderhoof, 1999, Arvola, 1999, Johnston, 2006, Goldenberg, 2015. Besides, a dose of *Lactobacillus rhamnosus* GG in LRG-002 product corresponds to the doses recommended in the published guidelines of the World Gastroenterological Organization (WGO, 2017) and the European Society of Pediatric Gastroenterologists, Hepatologists and Nutritionists (ESPGHAN, 2016).

According to the recommendations of the World Gastroenterological Organization, given in the international guidelines on probiotics and prebiotics (WGO, 2017) considering dosage in the case of antibiotic-induced diarrhea, the recommended dose of *Lactobacillus rhamnosus* GG for children is  $1-2 \times 10^{10}$  CFU, and for adults  $10^{10}$  CFU twice daily.

The developed product contains at least  $10^{10}$  CFU of *Lactobacillus rhamnosus* GG per capsule.

The investigational medicinal product and placebo in the frameworks of this study in accordance with the draft instructions for medical use of LRG-002 medicinal product will be prescribed according to the following scheme:

Single dose - 1 capsule; the investigational medicinal product/placebo will be taken orally 2 times a day (morning and evening) for 14 days. The tested product / placebo capsule is swallowed with some water. In case Visit 1 took place in the afternoon, only one capsule is allowed on the first day.

The medicinal product is recommended to be taken with meals, as this ensures its maximum efficacy, not less than 3 hours after taking antibiotics.

It must not be taken concomitantly with alcohol, fruit juices or hot beverages.

### **3.5.2 Justification of placebo use**

Due to the need for blinding of this study, a placebo will be used in the form of capsules for oral administration. The use of placebo is necessary for formation of objective conclusions about the efficacy and safety of the investigational medicinal product and is a standard practice. Efficacy of probiotic strains in comparison with placebo is shown in a number of clinical studies.

In this study, patients will not be exposed to the excess risk associated with placebo, as they will receive antibacterial therapy of the underlying disease.

Thus, the use of placebo in the study does not threaten the safety of patients and is fully consistent with international practice in clinical trials.

### **3.5.3 Regulatory frameworks**

This document is a clinical trial protocol, which is planned in accordance with the principles of the World Medical Association Declaration of Helsinki (Adopted by the 18th World Medical Assembly in Helsinki in June 1964, the latest revision was approved at the 64th Assembly in Fortaleza in October 2013), the Tripartite Guideline for Good Clinical Practice (GCP, ICH E6 (R2) dated 11/09/2016) and is regulated by the current legislation of the Eurasian Economic Union (EAEU) and the Russian Federation (RF):

- The rules of marketing authorization and assessment of medicinal products for medical use (approved by Decision No.78 of the Council of the Eurasian Economic Commission dated November 3, 2016);
- The rules of Good clinical practice of the Eurasian Economic Union (approved by Decision of the Council of the Eurasian Economic Commission dated November 3, 2016 No. 79);
- Federal law No. 61-FZ dated 12.04.2010 "On circulation of medicines" (in the current edition);
- Federal law No. 152-FZ dated 27.07.2006 "On personal data" (in the current edition);

- Order of the Ministry of Health of the Russian Federation dated April 1, 2016, N 200n “On Good Clinical Practice Approval”;
- Russian Federation national standard GOST R 52379-2005 "Good clinical practice”;
- Resolution of the government of the Russian Federation No.714 dated 13.09.2010 (as amended and supplemented) "On approval of standard rules of compulsory life and health insurance of a patient participating in clinical trials of a medicinal product”;
- The order of the Ministry of health of the Russian Federation No. 986n dated November 29, 2012 “Approval of the Regulations of the Board of Ethics” (in the current edition).
- The order of the Federal Service for Surveillance in the Health Care Sector (“Roszdravnadzor”) of the Russian Federation No. 1071 dated February 15, 2017, “On approval of the pharmacovigilance procedure”

### **3.6 Description of study population**

Men and women aged 18 to 65 years old with acute respiratory disease who signed an informed consent to participate in the study, meeting the inclusion criteria (see section 6.1.) and not having the criteria for non-inclusion (see section 6.2.)

## **4 Study aims and objectives**

### **4.1 Study goal**

The goal of this study is to investigate the efficacy and safety of LRG-002 investigational medicinal product, capsules (Lek d.d., Slovenia) in comparison with placebo, as an adjunct treatment for prophylaxis of antibiotic-associated diarrhea (AAD) in patients with acute respiratory diseases (ARDs) receiving a standard antimicrobial therapy.

### **4.2 Study objectives**

Main objective:

To evaluate the incidence of AAD while taking LRG-002, hard capsules (Lek d.d., Slovenia), as compared to placebo in antibiotic-treated patients with ARDs, receiving standard antimicrobial therapy;

Secondary objective:

To evaluate the safety of LRG-002 therapy, hard capsules (Lek d.d., Slovenia), as compared with placebo in antibiotic-treated patients with ARDs, receiving standard antimicrobial therapy.

## 5. Study Design

### 5.1 Main and additional studied parameters

#### 5.1.1 Efficacy parameters

##### 5.1.1.1 Primary efficacy parameter

An assessment of frequency of occurrence of AAD from 1 to the last day of LRG-002 administration compared with placebo in antibiotic-treated patients with ARDs, receiving standard antimicrobial therapy is selected as the primary efficacy endpoint. The primary efficacy criterion will be considered achieved if the odds ratio for the AAD incidence between two groups is significantly higher than 1 (i.e. AAD incidence in the LRG-002 group is lower than in placebo group).

*AAD is defined as diarrhea associated with the AB use caused by C. difficile or of otherwise not identified etiology, upon analysis of stool samples and differential diagnostics according to investigator's judgment.*

*Diarrhea is defined as loose or watery stool (Type 5-7 according to Bristol Stool Form Scale) three times a day (frequent bowel movements with formed stool is not considered as diarrhea) in accordance with WHO criteria; based on the diary data (BSFS) and confirmation of AAD by the investigator.*

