|  | 

• 1 container – stool sample for presence of C. difficile toxins A and B;

• 1 container – stool sample for culture for opportunistic flora: Klebsiella pneumoniae, Staphylococcus aureus, Proteus mirabilis, Candida spp, E. Coli and for culture Yersinia spp (special container).

 
Visit 2
 

• Dispensing of laboratory kit with the necessary supplies to collect stool samples (if necessary):

 
Stool sample collection in case of diarrhea (between V2 and V3):
 

• 1 container – stool sample for presence of common diarrheal pathogens (rotavirus, adenovirus, norovirus, Campylobacter spp, Salmonella spp, Shigella spp);

• 1 container – stool sample for presence of C. difficile toxins A and B;

• 1 container – stool sample for culture for opportunistic flora: Klebsiella pneumoniae, Staphylococcus aureus, Proteus mirabilis, Candida spp, E. Coli and for culture Yersinia spp (special container).

 
Visit 3
 

• Collection of unused laboratory kit (in case there was no diarrhea between V1 and V3).

 
In case of diarrhea between visits, the patient must contact the site and collect stool samples in three containers (containers are received at V1 and V2). The site employee arrives at the patient to collect containers in thermo package and transport them to the laboratory.
 
In the case of acute diarrhea (loose, watery stool [BSFS Type 6, 7] with an occurrence of 3 or more times within 24 hours), the patient should contact the investigator for advice on therapy.
 
Unscheduled Visits
 
The unscheduled visits will be conducted when necessary, e.g., in case of the index disease deterioration, AEs, or intolerability of IMPs (LRG-002 or placebo).
 |
|--|---|

|  |  |
|--|--|

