##### 5.1.1.2 Secondary efficacy parameters

The following criteria were selected as secondary efficacy criteria of the therapy in all study groups for a comparative assessment of the therapeutic effect:

- The occurrence of bowel movements per day (according to the diary data) in the treatment group compared with the placebo group;
- The incidence of any diarrhea in the treatment group compared with the placebo group;
- The incidence of C. difficile-associated AAD in the treatment group compared with the placebo group;
- The incidence of AAD not associated with C. difficile in the treatment group compared with the placebo group;
- The duration of AAD (the time from the onset of AAD to the normalization of stool form according to BSFS (types 1, 2, 3 and 4) and the presence of normal stool within 48 hours)) in the treatment group as compared to the placebo group;

- Duration of any diarrhea (the period from the diarrhea onset to the normalization of stool form according to BSFS (types 1, 2, 3 and 4) and the presence of normal stool within 48 hours)) in the treatment group vs the placebo group;
- The changes in stool consistency (according to Bristol Stool Form Scale) (according to the diary data) in the treatment group as compared to the placebo group;
- The changes and severity of gastrointestinal symptoms, including nausea, vomiting, flatulence, abdominal pain and decreased appetite (according to the diary data) in the treatment group as compared to the placebo group;
- Change in body weight at Visit 3 compared with Visit 1 in the placebo group as compared to the treatment group;
- Hospitalization rate in the treatment group compared with the placebo group;
- The number of days of using standard symptomatic therapy (as “rescue medication”) to relieve symptoms of acute diarrhea in the treatment group as compared to the placebo group;
- The number of patients using standard symptomatic therapy (as “rescue medication”) to relieve symptoms of acute diarrhea in the treatment group as compared to the placebo group.

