## **17.2. Appendix 2. Prescribing on stool sample collection for patient**

**In case of diarrhea, collect samples of the stool according to the following instructions:**

### **Container 1 (sterile container with spoon and lid).**

Collect a stool sample of no more than 1/3 of the container volume (from several places). During collection, try to avoid impurities of urine and urethral and vaginal discharge. Close the container, place it to the fridge (NOT to the freezer).

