**3. Occurrence of stool a day; consistency of stool**

Mark the time each chair episode occurred today and indicate the type of consistency (see Figure 1).

1. Time: \_\_\_\_\_  
Type 1234567

2. Time: \_\_\_\_\_  
Type 1234567

3. Time: \_\_\_\_\_  
Type 1234567

4. Time: \_\_\_\_\_  
Type 1234567

5. Time: \_\_\_\_\_  
Type 1234567

6. Time: \_\_\_\_\_  
Type 1234567

7. Time: \_\_\_\_\_  
Type 1234567

8. Time: \_\_\_\_\_  
Type 1234567

9. Time: \_\_\_\_\_  
Type 1234567

10. Time: \_\_\_\_\_  
Type 1234567

Comments \_\_\_\_\_ and  
complaints: \_\_\_\_\_

If you notice a loose stool or watery shapeless stool with a frequency of 3 or more times a day, you should call and inform your doctor. Your doctor will recommend the drugs approved for use in this study to eliminate symptoms of your condition.

Please remember that the decision to take additional drugs can only be made by a doctor.

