**17.4. Appendix 4. Bristol Stool Form Scale (according to Lewis S. J. Et al, 1997, adapt. by Kharchenko et al. 2007)**

| Type of consistency | Parameter   | Figure  |
|---------------------|---|---|
| Type 1       | individual hard lumps like nuts (passageway is difficult) |    |
| Type 2       | sausage like stool, but lumpy                             |    |
| Type 3       | sausage shaped feces with cracks in the surface           |    |
| Type 4       | smooth and soft sausage or snake shaped feces             |    |
| Type 5       | Soft blobs with clear-cut edges                           |    |
| Type 6       | loose pieces with ragged edges                            |   |
| Type 7       | loose stool   |  |

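### The Visit 3 window opens on Day 13, before the 14-day regimen and the primary endpoint period end; as a minor point, the patient's stool-sampling sheet does not define diarrhea although the endpoint counts Bristol types 5-7

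*Protocol*

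**What the plan says.** **Visit 3 and the regimen.** Protocol Section 5.2.4.3 holds Visit 3 in the morning of Day 15 ± 2 and lists collection of the diary and unused product. Section 5.7 and SAP Sections 2.2.2 and 2.2.3 repeat the ± 2 window. Section 5.5 schedules capsules twice a day through Day 14 (one or two on Day 1). Section 6.3.2 has patients stop the product when participation ends. The primary endpoint in Section 5.1.1.1 runs from Day 1 to the last day of administration. The Synopsis, under planned study duration, labels Visit 3 as following completion of the regimen. Diary pages in Appendix 3 run to Day 17.

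**Stool type and sampling.** The endpoint rule in Section 5.1.1.1 is: "Diarrhea is defined as loose or watery stool (Type 5-7 according to Bristol Stool Form Scale) three times a day". AAD is then diarrhea linked to the antibiotic and "caused by C. difficile or of otherwise not identified etiology, upon analysis of stool samples and differential diagnostics", with the investigator's judgment. The duration endpoints in Section 5.1.1.2 end at "normalization of stool form according to BSFS (types 1, 2, 3 and 4"), so type 5 is not yet normal. For sampling, the Synopsis says: "In case of diarrhea between visits, the patient must contact the site and collect stool samples in three containers". Appendix 2, the sheet written for the patient, begins: "In case of diarrhea, collect samples of the stool according to the following instructions", with no stool type and no count. The diary prompt reads: "If you notice a loose stool or watery shapeless stool with a frequency of 3 or more times a day, you should call". Appendix 4 words type 5 as "Soft blobs with clear-cut edges" and uses the word loose for types 6 and 7. Types 6-7 also define acute diarrhea in the Synopsis and Section 5.2.3.2.5; there the Synopsis says "the patient should contact the investigator for advice on therapy".

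**The concern.** Visit 3 ends both dosing and diary recording. If it takes place on Day 13 or 14, the site is inside the stated window and yet the patient has not had the planned 14 days. The length of the primary endpoint period then depends on the appointment date. The per-protocol set requires completion of the planned treatment and follow-up (Protocol Section 10.8, SAP Section 4.2.3), so it is also unclear whether such a patient belongs to it. The Synopsis ties the minimum of 208 per arm to that set.

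The stool-type point is about whether a sample exists. A patient has to recognise diarrhea at home and act on it. One who matches the diary prompt to the Appendix 4 wording could reasonably leave type 5 out. The diary would still show the episode, but it is reviewed at Visits 2 and 3, possibly too late to collect a stool from that episode. Protocol Section 8.2 bases two secondary endpoints, AAD with and without C. difficile, on the stool analysis, and nothing else can supply that result.

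**Working it through.** **1. Visit window.** Inputs: Day 15 ± 2 (Section 5.7), morning (Section 5.2.4.3), dosing on Days 1-14 (Section 5.5).
- Permitted days: 15 - 2 = 13 to 15 + 2 = 17, which is five days. Days 13 and 14 are 2 of these 5.
- Morning of Day 13: 12 full treatment days are complete, or 12 × 2 = 24 of 14 × 2 = 28 capsules if two were taken on Day 1. Up to 2 of 14 days are lost.
- Morning of Day 14: the evening capsule and the rest of that day's record are lost.
- Days 15 to 17: nothing is lost, and the diary has pages for these days.
- Each patient counts once for AAD (Section 10.1.2), so the primary endpoint changes only if a first AAD episode would have fallen on the lost days. The documents give neither the spread of visit dates nor the timing of onset, so the number of patients and events affected cannot be derived.

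**2. Stool type, place by place.**
- Endpoint (5.1.1.1): types 5, 6 and 7, three times a day.
- Sampling, protocol body (Synopsis, 5.2.3.2.5): diarrhea, which is the protocol's defined term and so includes type 5.
- Sampling, patient sheet (Appendix 2): diarrhea, undefined.
- Diary prompt (Appendix 3): loose or watery shapeless stool, no Bristol type.
- Acute diarrhea, for contact and therapy (Synopsis, 5.2.3.2.5): types 6 and 7.

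The protocol body is consistent on sampling. The gap is in what the patient holds.

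**3. Sample size, and an illustration only.** The plan's figure reproduces: ((1.960 + 0.842) / 0.11)² × (0.15 × 0.85 + 0.26 × 0.74) = 207.5, rounded up to 208 per arm; 208 / 0.8 = 260 randomized per arm.

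Assume, with no support in the documents, that a share f of true AAD episodes is lost equally in both arms. The rates become 0.15(1 - f) and 0.26(1 - f), and power = Φ(difference / SE - 1.960), where SE = √{[p_T(1 - p_T) + p_R(1 - p_R)] / n}. For f = 10% the rates are 0.135 and 0.234, and z = 2.624 at 208 per arm.

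| f | power, 208 per arm | power, 260 per arm |
|---|---|---|
| 0% | 80.1% | 88.0% |
| 5% | 77.5% | 85.9% |
| 10% | 74.7% | 83.5% |
| 20% | 68.5% | 77.9% |

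The value of f is unknown and may be 0. The table shows what would follow from a loss; it does not estimate one.

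**The case against.** On Visit 3, the Synopsis already states the intent, and the diary runs past Day 14. The endpoint is also worded to the last day of administration, so if dosing stops early the observation stops with it and nothing is formally missing. The first part shows intent, but the operative visit sections and the SAP carry the ± 2 window without that qualifier. The last part only means that the observation period varies with the appointment. A reader might infer that two-fifths of patients lose days. The documents do not support this: 2 of 5 counts calendar days, not patients.

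On stool type, several objections stand.
- A reader might infer that the protocol contradicts itself on when to sample. It does not: types 6-7 belong to the separate acute-diarrhea text, which concerns contact and therapy.
- The diary argument rests on fine distinctions of wording in what may be a translation, and the figure to which the diary refers is not in the text available here. Visit 1 training and the instructions given with the containers may close the gap, though their content is not stated.
- A reader might infer a loss of power for the primary endpoint. That requires episodes that are type 5 only, unsampled and then rejected as AAD. The AAD definition includes diarrhea without an identified cause, so the investigator may accept these episodes, and over-counting is as plausible as loss. Sections 10.6 (Protocol) and 3.2 (SAP) also allow likelihood-based filling of missing primary-endpoint values, although in general terms.
- A reader might infer bias toward one arm. Both arms are blinded and receive the same instructions, so nothing points that way.
- The C. difficile split is exploratory, without multiplicity adjustment or formal power (Protocol Section 10.1.3, SAP Section 7.2).

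**Conclusion.** The Visit 3 conflict holds. A visit inside the stated window can cut up to 2 of 14 days from treatment and from the primary endpoint period, and leaves per-protocol membership open to question. The share of patients is unknown. Nothing suggests a difference between arms, so the expected cost is completeness of the endpoint.

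The stool-type point holds as a minor one. The patient's sampling sheet lacks the endpoint definition, and the diary prompt does not clearly cover type 5. Some type-5-only episodes may therefore reach the investigator without a stool result. This mainly weakens the exploratory C. difficile split. The incidence of any diarrhea does not depend on etiology and is not affected. For the primary endpoint the effect is unknown and may be zero; the power figures above are illustrations under an assumed loss and are not a finding.

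**What to change.** 1. Reconcile the Visit 3 window with the 14-day regimen in the Synopsis, Protocol Sections 5.2.4.3 and 5.7 and SAP Sections 2.2.2 and 2.2.3, so that the visit and diary collection do not precede the end of the planned endpoint period. The diary pages to Day 17 and the 17-day limit already allow for later visits. The cost is less flexibility in scheduling.
2. Copy the protocol's own endpoint definition (types 5-7, three times a day) into Appendix 2 as the trigger for stool sampling only. The cost is extra samples from mild episodes, each with three containers and a staff collection, and possibly more kits, since the second kit at Visit 2 is given only if needed.
3. Leave the type 6-7 contact and therapy passages and the diary call prompt for the sponsor to reconcile. This review proposes no threshold for contact or treatment.
4. Report by arm the number of diary-positive episodes without a stool result. This is one added table.

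Items 1 and 2 need a short protocol amendment with regulatory and ethics approval (Section 11.2); items 1 and 4 need a small SAP edit.
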